#### D. Analysis

##### (1) General

This section outlines the statistical analysis strategy and procedures for the study. Descriptive statistics will primarily be generated to summarize the data. For continuous variables, descriptive statistics may include the number of subjects reflected in the calculation (n), mean, standard deviation, median, minimum, and maximum; frequencies and percentages may be displayed for categorical data. A detailed Statistical Analysis Plan (SAP) will be generated before the data analysis will be conducted.

##### (2) Analysis of Primary Endpoints

*PSA complete response:* PSA complete responses will be analyzed by descriptive statistics and summarized in tabular format (frequency tables). The PSA complete response rate will be estimated using the Whitehead's bias adjustment method which takes into account the sequential testing procedure of the proposed two-stage design. The table below shows the estimated objective response rates, the p-values and 90% confidence intervals for various scenarios:

**Table 2: Estimated PSA complete response rates, p-values and confidence intervals**

Number of PSA complete responses	Estimated PSA complete response rate †	p-value	Lower 95% CI bound	Upper 95% CI bound
0	0.0%	1.0000	0.0%	0.0%
1	5.7%	0.6590	0.2%	13.3%
2	5.9%	0.2830	1.7%	20.7%
3	8.5%	0.2120	2.6%	20.8%
4	10.9%	0.1140	3.7%	21.3%
5	13.2%	0.0460	5.1%	22.7%
6	15.4%	0.0140	6.7%	24.8%

7	17.7%	0.0040	8.4%	27.2%
8	20.0%	0.0010	10.1%	29.8%
9	22.3%	0.0000	12.0%	32.5%
10	24.6%	0.0000	13.9%	35.2%

† Estimated using Whitehead's bias-adjustment approach

For example, if at the end of the study, PSA complete response efficacy responses are observed in 5 out of the 41 patients, then the estimated (bias adjusted) response rate is 13.2% with a 95% confidence intervals ranging from 5.1% to 22.7%.

A minimum of 5 complete PSA responses are required to reject the null hypothesis which warrants further clinical investigation.

*Toxicity and adverse events:* Subjects will be evaluated at each visit by a review of systems based on the most recent version of the NCI common toxicity criteria. Toxicities will be summarized by type and severity in tabular format. Toxicity rates (grade 2, grade 3, grade 4, grade  $\geq$  2, grade  $\geq$  3, etc.) will be calculated and reported along the corresponding 95% confidence intervals. The 95% confidence intervals will be constructed using the Wilson score method.

### (3) Analysis of Secondary Endpoints

*2-year metastasis-free Survival Rate:* The 2-year metastasis-free survival rate will be estimated using the Kaplan-Meier method and reported along with the corresponding two-sided 95% confidence interval.

*Median radiographic progression-free survival:* Radiographic progression-free survival will be estimated using the Kaplan-Meier method. The Brookmeyer-Crowley method will be used to construct the 95% confidence interval of the median radiographic progression-free survival.

*PSA doubling time:* PSA doubling time will be estimated for each patient using linear regression analysis. Specifically, PSA doubling time will be calculated as  $\log(2)$  divided by the slope parameter of the regression of  $\log(\text{PSA})$  on time. PSA doubling times and slopes will be summarized in terms of means, medians, standard deviation, and 95% confidence interval. Changes in PSA doubling time and slopes will be evaluated using a paired t-test or nonparametric Wilcoxon Signed Rank test.

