### 5. Patient Selection

#### A. Inclusion Criteria

1. Patients must be at least 18 years of age with a histologic diagnosis of adenocarcinoma of the prostate
2. Patients must have undergone radical prostatectomy
3. Patients must have completed local therapy by surgery and any adjuvant/salvage radiation therapy at least 3 months prior to entry, with removal or ablation of all visible disease, including seminal vesical and/or local lymph node involvement.

4. Patients must have biochemically recurrent, non-metastatic (by CT and bone scan) clinical stage D0/M0 disease defined by the following:
  - Patients must have evidence of detectable serum PSA with at least 4 serum PSA measurements available, from the same clinical laboratory, at least two weeks apart up to one year, and the final serum PSA value must be  $\geq 2.0$  ng/mL.
  - PSA doubling time, calculated from most recent 4 serum PSA values (collected up to one year prior to enrollment, at least 2 weeks apart, and all from the same clinical laboratory), must be a positive number (i.e. evidence of PSA rise over time).
  - PSA doubling time will be calculated using the Memorial Sloan-Kettering Cancer Center nomogram:  
(<http://www.mskcc.org/applications/nomograms/prostate/PsaDoublingTime.aspx>).
  - Patients must not have definitive evidence of metastases as determined by CT of the abdomen/pelvis and bone scintigraphy (bone scan). Note: patients with lesions detectable by highly sensitive methods (e.g. NaF PET imaging or PSMA PET imaging) will be considered eligible as long as these lesions do not meet size criteria on CT imaging (visceral lesions suspicious for metastases or lymph node  $> 15$  mm in short axis) and/or are not independently observed on bone scan.
5. Patients with a prior history of a second malignancy are eligible provided they have been treated with curative intent and have been free of disease greater than three years. There will be no exclusion for patients with a history of basal cell carcinoma, squamous cell skin cancer, superficial bladder cancer, or other *in situ* carcinoma that has been adequately treated.
6. Patients who are sexually active must use a reliable form of contraception while on study and for 4 weeks after the last immunization.
7. ECOG performance score  $< 2$  and life expectancy of at least 12 months.

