- (1) All PSA values obtained from the same clinical laboratory using the same PSA assay beginning with the PSA value at day 1 (week 0) and continuing until the end-of study (or month 24) value (PSADT0-24).
- (2) All PSA values obtained from the same clinical laboratory using the same PSA assay beginning with the PSA value at day 85 (month 3) to the day 253 (month 9) value (PSADT3-9).

These time points for PSADT assessment were chosen to correspond to those being obtained in a randomized phase 2 trial using the pTVG-HP vaccine alone (NCT01341652).

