#### C. Serum PSA Doubling Time Evaluation

See Section 11 for further details. Serum PSA doubling-time (or PSA slope) response will be considered a secondary endpoint. The pre-treatment serum PSA doubling time will be calculated from four serum PSA values available from the same clinical laboratory using the same assay for the period up to one year prior to study treatment, not on other treatments for prostate cancer, up to and including the PSA value obtained at screening, using the Memorial Sloan-Kettering Cancer Center nomogram

(<http://www.mskcc.org/applications/nomograms/prostate/PsaDoublingTime.aspx>). The post-treatment PSA doubling time will be calculated using the same nomogram from:

- (1) All PSA values obtained from the same clinical laboratory using the same PSA assay beginning with the PSA value at day 1 (week 0) and continuing until the end-of study (or month 24) value (PSADT0-24).
- (2) All PSA values obtained from the same clinical laboratory using the same PSA assay beginning with the PSA value at week 12 (month 3) to the week 36 (month 9) value (PSADT3-9).

An increase in the PSA doubling time to at least double the baseline value, and at least 15 months, will be considered a PSA doubling time “response” [7].

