### (4) Exploratory Objectives

The number of antigen-specific T-cell and/or IgG responses will be summarized in terms of means, standard deviations, medians and ranges for each assessment time point. Changes from baseline will be evaluated using a nonparametric Wilcoxon Signed Rank test. A negative binomial or overdispersed Poisson model (depending on the model fit) will be utilized to evaluate whether antigen-specific T-cell and/or IgG responses are elicited with treatment. Univariate and multivariate logistic regression analysis will be conducted to examine whether the development of PAP-specific T-cell immune responses and antigen spread are associated with PSA response.

**Results from the QTBI analysis will be used to determine (1)** whether QTBI by NaF PET/CT can identify bone lesions in this patient population not detected by standard bone scintigraphy, (2) whether the presence of lesions detected by NaF PET/CT at baseline is associated with early disease progression (within 1 year) by standard radiographic imaging methods (CT and bone scintigraphy), and (3) whether growth rates, and changes in growth rates, determined by NaF PET/CT are associated with PSA doubling time and changes in PSA doubling time. Sensitivity of QTBI by NaF PET/CT to identify bone lesions will be summarized in tabular format and compared to sensitivity of standard bone scintigraphy using a paired McNemar's test. Univariate and multivariate Cox proportional hazard regression analyses will be conducted to evaluate the associations between presence of lesions detected by NaF PET/CT at baseline and time to disease progression. Analogously, univariate and multivariate logistic regression analyses will be performed to evaluate the associations between presence of lesions detected by NaF PET/CT at baseline and 1-year PFS rate. The associations between changes in QTBI parameters (SUVmax, SUVmean, SUVtotal) and changes in PSA doubling time will be evaluated using linear mixed effects modeling with subject specific random effects.

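### The PSA doubling-time analysis has no rule for a flat or falling PSA, so the best outcomes are scored as worsening and as non-response

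*Combined protocol and SAP*

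**What the plan says.** Section 10.D(3) defines PSADT as log(2) "divided by the slope parameter of the regression of" log(PSA) on time. It continues: "PSA doubling times and slopes will be summarized in terms of means, medians, standard deviation, and 95% confidence interval", and then: "Changes in PSA doubling time and slopes will be evaluated using a paired t-test or nonparametric Wilcoxon Signed Rank test". It sets no condition on the sign of the slope.

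Section 9.C treats PSADT (or slope) response as a secondary endpoint and gives the rule: "An increase in the PSA doubling time to at least double the baseline value, and at least 15 months, will be considered" a response. It does not use regression: "The post-treatment PSA doubling time will be calculated using the same nomogram from" two sets of values, one for months 0-24 and one for months 3-9. The first set is described in section 6.B as "beginning with the PSA value at day 1 (week 0) and continuing until the end-of study (or month 24) value". Section 9.C does not say which window decides response.

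The only rule on sign is for entry. Under section 5.A the pre-treatment doubling time "must be a positive number (i.e. evidence of PSA rise over time"). Section 10.D(4) also carries PSADT into the bone-imaging analysis, where associations between QTBI parameters and "changes in PSA doubling time will be evaluated using linear mixed effects modeling with subject specific random effects".

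**The concern.** Log(2)/slope is discontinuous at zero. As growth slows, PSADT rises without limit. Once PSA starts to fall, it jumps to a large negative number and then moves back towards zero as the fall steepens. The scale therefore reverses the clinical order where the treatment works best.

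Falling PSA is foreseeable here. The primary efficacy endpoint is a PSA complete response, a decline of at least 50% is a listed secondary endpoint, and section 2.E reports PSA declines in about half of the patients given the vaccine concurrently with a PD-1 antibody in a related trial. That trial had a different disease stage and antibody, and a decline at some time point is not the same as a negative fitted slope, but the case clearly needs a rule.

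At stake are the PSADT means, SDs and tests, the PSADT response classification, and the QTBI association with change in PSADT. A complete responder could be listed as a PSADT non-responder, and the PSADT test could contradict the slope test reported beside it, with no stated priority between them.

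**Working it through.** The plan gives no expected value, sample size or power for PSADT, so there is no figure of its own to reproduce. The check applies its formula and response rule to worked PSA courses and then simulates the tests.

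**1. Sign.** Entry makes baseline PSADT positive. If the post-treatment slope is negative, PSADT = log(2)/slope < 0. The change (post minus baseline) is then negative, and both parts of the response rule fail. No effect size is assumed.

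**2. Around zero.** Assume a baseline PSADT of 6 months, so the baseline slope is log(2)/6 = 0.1155 per month.

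| Post-treatment course | PSADT (months) | Change in PSADT | Change in slope per month | Response by 9.C |
|---|---|---|---|---|
| Rise, doubling in 18 months | +18 | +12 | -0.077 | yes |
| Rise, doubling in 200 months | +200 | +194 | -0.112 | yes |
| Fall, halving in 200 months | -200 | -206 | -0.119 | no |
| Fall of 50% over 96 weeks | -22.1 | -28.1 | -0.147 | no |
| Fall from 2.0 to 0.19 over 96 weeks | -6.5 | -12.5 | -0.222 | no |

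The slope column orders the five courses correctly. The PSADT column does not.

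**3. A complete responder.** Fit log(PSA) by least squares at weeks 0, 4, 8, ..., 48, 60, 72, 84 and 96 (the section 8 visits; 4.345 weeks per month). PSA falls log-linearly from 2.0 to 0.1 ng/mL by week 12 and stays there. This meets the confirmed PSA CR definition if there is no radiographic progression.
- Months 0-24: slope -0.0706 per month, PSADT = 0.693/(-0.0706) = -9.8 months, non-response.
- Months 3-9 (weeks 12-36): slope 0, PSADT undefined.

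**4. The two windows can disagree.** PSA halves every 12 months to week 48, then doubles every 6 months.
- Months 0-24: slope +0.0206, PSADT +33.7 months. This is a response from a 6-month baseline.
- Months 3-9: slope -0.0578, PSADT -12.0 months, non-response.

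**5. Simulation.** These inputs are assumptions, not from the documents: baseline PSADT log-normal with median 9 months and log-SD 0.6; slope standard error 0.01 per month before and after treatment; two-sided 5% tests; n = 41; 2,000 runs per scenario. Power counts significant results in the correct direction. Missed means the patient meets the rule restated in slopes but fails it in PSADT.

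| Slope reduction, mean/SD | Negative slopes | PSADT t-test | PSADT Wilcoxon | Slope t-test | Responders missed |
|---|---|---|---|---|---|
| (a) 30%/30% | 2% | 30% | 98% | >99% | 10% |
| (b) 50%/50% | 17% | 2% | 33% | >99% | 38% |
| (c) 70%/60% | 31% | 1% | 3% | 100% | 54% |

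The response rate in (b) is 28% by the PSADT rule and 46% on the slope scale; in (c) it is 27% and 58%. Ranking non-positive slopes as the best outcome restores Wilcoxon power to above 99% in all three.

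Sensitivity for (b), with baseline median 6-12 months and slope standard error 0.005-0.02: PSADT Wilcoxon 3%-50%, slope test at least 99%, 35%-46% missed. At n = 21 (stage 1 only): PSADT t-test 2.5%, Wilcoxon 19%, slope t-test 95%, 38% missed.

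**6. A different assumed model.** Significant wrong-direction PSADT results are 3% or less in (a) to (c). That is not general. Take a baseline median of 6 months, risers with a median doubling time of 8 months, fallers with a median halving time of 10 months, and log-SD 0.4 throughout. With half the patients falling, the mean PSADT change is -7.6 months. The t-test shows significant worsening in 99.5% of runs and Wilcoxon in 94.8%, while Wilcoxon on slopes shows improvement in 100%.

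**The case against.** **The objective already has a sound test.** It is worded as change in doubling time or slope, and section 10.D(3) tests slopes in the same sentence. This stands, and it limits the damage to the PSADT scale. But the response rule and the QTBI association have no slope counterpart.

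**Response feeds no planned analysis.** Section 10.D(3) indeed plans no estimate or test of a PSADT response rate. Section 9.C nevertheless defines the response and names it a secondary endpoint, so it will be classified and probably reported.

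**A later SAP or the nomogram may settle it.** Section 10.D(1) promises a detailed SAP before analysis, and how the nomogram treats falling PSA cannot be seen from the documents. The automatic non-response therefore rests on reading the 10.D(3) formula with the 9.C rule. But this is an open-label, single-arm trial in which PSA is seen throughout and guides GM-CSF use at week 4. A rule chosen once the PSA courses are known is open to challenge.

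**The magnitude is assumed, and part of the t-test loss has another cause.** Both points stand. With non-positive slopes dropped, PSADT t-test power is still only about 66%, 60% and 53% in (a), (b) and (c), because the reciprocal of a small positive slope has a heavy tail. In (a), the Wilcoxon option already allowed gives 98%. The signs and classifications in steps 1 to 4 do not depend on the simulation.

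**Conclusion.** The concern holds. Given the positive baseline that entry requires, the stated formula and response rule score every negative post-treatment slope as a negative change and a non-response, and they leave a zero slope undefined. Wilcoxon does not rescue the test, because those changes rank on the worsening side.

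The size depends on how many fitted slopes are negative. Under the assumed scenarios with 2% to 31% negative, 10% to 54% of slope-equivalent responders are missed and PSADT Wilcoxon power drops from 98% to 3%. With about half negative, the PSADT test can point significantly the wrong way. All these percentages rest on assumed effect sizes.

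The defect is confined to the PSADT part of a secondary objective and one exploratory association. The slope analysis, the PSA CR rate, the 50% PSA response and the go/no-go decision are untouched. It should be corrected before analysis.

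**What to change.** - Make the log(PSA) slope the scale for the test of change and for the QTBI association.
- Restate response in section 9.C as a post-treatment slope no more than half the pre-treatment slope and no more than log(2)/15 = 0.0462 per month. For positive slopes this equals the current rule; zero and negative slopes become responses.
- State which window, months 0-24 or 3-9, decides response.
- Report PSADT descriptively by its median, with non-positive slopes shown as not rising and ranked best. If a PSADT test is kept, use Wilcoxon with that ranking.
- Reconcile the nomogram in 9.C with the regression in 10.D(3) and name one method.

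The cost is wording in sections 9.C, 10.D(3) and 10.D(4) and in the later SAP. The slopes are already computed, and no data collection or sample size changes.

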### (4) Exploratory Objectives

The number of antigen-specific T-cell and/or IgG responses will be summarized in terms of means, standard deviations, medians and ranges for each assessment time point. Changes from baseline will be evaluated using a nonparametric Wilcoxon Signed Rank test. A negative binomial or overdispersed Poisson model (depending on the model fit) will be utilized to evaluate whether antigen-specific T-cell and/or IgG responses are elicited with treatment. Univariate and multivariate logistic regression analysis will be conducted to examine whether the development of PAP-specific T-cell immune responses and antigen spread are associated with PSA response.

**Results from the QTBI analysis will be used to determine (1)** whether QTBI by NaF PET/CT can identify bone lesions in this patient population not detected by standard bone scintigraphy, (2) whether the presence of lesions detected by NaF PET/CT at baseline is associated with early disease progression (within 1 year) by standard radiographic imaging methods (CT and bone scintigraphy), and (3) whether growth rates, and changes in growth rates, determined by NaF PET/CT are associated with PSA doubling time and changes in PSA doubling time. Sensitivity of QTBI by NaF PET/CT to identify bone lesions will be summarized in tabular format and compared to sensitivity of standard bone scintigraphy using a paired McNemar's test. Univariate and multivariate Cox proportional hazard regression analyses will be conducted to evaluate the associations between presence of lesions detected by NaF PET/CT at baseline and time to disease progression. Analogously, univariate and multivariate logistic regression analyses will be performed to evaluate the associations between presence of lesions detected by NaF PET/CT at baseline and 1-year PFS rate. The associations between changes in QTBI parameters (SUVmax, SUVmean, SUVtotal) and changes in PSA doubling time will be evaluated using linear mixed effects modeling with subject specific random effects.

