In the setting of PSA recurrence after definitive therapy, this stage D0/M0 being evaluated, it is assumed that patients have metastatic disease that is simply below the level of current methods of detection. We and others have demonstrated that NaF PET/CT provides a more sensitive method of detecting bone metastases in patients with more advanced prostate cancer {Morisson, 2013 #4088}, suggesting that this method may be more sensitive in detecting minimal residual disease in the setting of PSA recurrence. Moreover, NaF PET/CT can provide a more

quantitative assessment of total bone involvement, an assessment that cannot be determined from standard bone scintigraphy {Morisson, 2013 #4088}, when combined with advanced image analysis, such as in Quantitative Total Bone Imaging (QTBI), developed at University of Wisconsin Carbone Cancer Center. QTBI can be used to evaluate changes in total prostate cancer bone involvement over time, effectively a measure of tumor growth rate in bone. Our group explored the role of NaF PET/CT in a similar patient cohort in a subset of patients enrolled in a randomized phase II trial of pTVG-HP versus GM-CSF adjuvant in patients with non-metastatic prostate cancer (NCT01341652). Among 34 patients who had NaF PET/CT scans, only 4 of 34 did not have a lesion identified at baseline, and only 1 of 34 patients had no lesions at any time point. Although the median number of lesions detected and change in total activity ( $SUV_{total}$ ) was not significantly different for the two treatment cohorts, the median  $SUV_{total}$  increased 50.4% in the GM-CSF arm and decreased 23.0% in the pTVG-HP arm [manuscript under preparation].

In this study we wish to further explore, whether these methods could be used to identify individuals at particularly high risk for early disease progression and to evaluate whether treatment with a DNA vaccine in combination with nivolumab can affect the tumor growth rate analogous to changes in PSA doubling time. Moreover, we wish to determine whether the pattern of disease progression (continued growth of all lesions, or rapid growth of individual lesions) differs among patients based on their response to treatment.

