8. Patients must not have evidence of bone metastases or lymph node involvement as determined by bone scan or CT scan of the abdomen and pelvis within 4 weeks of study registration. Note: Advanced imaging modalities (such as NaF-PET/CT, choline PET/CT, fluviclovine, or PSMA PET scans) will NOT be used to determine evidence of metastases for eligibility purposes or for defining disease progression.
9. Patients must not have been treated with a prior DNA vaccine therapy for prostate cancer.
10. Patients must not have known psychological or sociological conditions, addictive disorders or family problems, which would preclude compliance with the protocol.
11. Patients must not have known allergic reactions to GM-CSF.
12. Patients with unstable or severe intercurrent medical conditions or laboratory abnormalities that would impart, in the judgment of the PI, excess risk associated with study participation or study agent administration.
13. Patients cannot have concurrent enrollment on other phase I, II, or III investigational therapeutic treatment studies.

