#### D. Quantitative Total Bone Imaging (QTBI) using NaF PET/CT

An assessment of small volume bone metastatic disease (potentially not detected by standard bone scintigraphy) and tumor growth rates will be conducted using QTBI. Patients selected to participate in the NaF PET/CT part of the study will be assessed at baseline, week 12, and week 24 by NaF PET/CT. Metastatic prostate cancer lesions in bone will first be localized and identified based on functional NaF PET uptake, assisted with the anatomical information

provided by CT scans. Segmentation will be performed using an automatic segmentation method (e.g. a fixed SUV threshold), and adjusted with physician guidance. Scans from different time points will be registered to one another using an articulated registration technique employing a rigid registration of skeletal elements (bones) from CT followed by registration optimization by combining with deformable registration of bones and lesions from NaF PET/CT. The lesions between pre-treatment and follow-up scans will be matched to establish longitudinal correspondence of the lesions. For each patient, comprehensive treatment response metrics will be calculated, consisting of SUVtotal (total disease burden), SUVmax (maximum intensity lesion), SUVmean (average intensity), the number of lesions, and total volume of bone lesions. In addition, imaging response metrics will be calculated for each individual lesion. This methodology will specifically be used to assess the growth rate of bone metastatic disease by evaluating changes from baseline to month 3 and from month 3 to month 6. In terms of logistics, each of the clinical centers has the capacity and expertise to perform NaF PET imaging.

NaF-PET/CT IMAGING PROCEDURES: To ensure uniformity as well as optimal data interpretation, a standardized image acquisition protocol will be utilized and the overall imaging analyses will be conducted centrally under the supervision of [name], PhD (co-investigator) at the University of Wisconsin Image Analysis Core (IMAC) facility, with all analysis blinded to study treatment arm. Please refer to the Standard Operating Procedures (SOP) document for NaF-PET/CT procedures, which will be adhered to at both sites, for details of image acquisition, image analysis, image interpretation, image submission for central review, and other imaging-related details.

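### At baseline the planned McNemar test of NaF PET/CT against bone scan can only favour NaF, and with no reference standard it does not measure sensitivity

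*Combined protocol and SAP*

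**What the plan says.** Section 10.D(4) sets the first imaging question as "whether QTBI by NaF PET/CT can identify bone lesions in this patient population not detected by standard bone scintigraphy". It then plans a tabular summary of NaF sensitivity, "compared to sensitivity of standard bone scintigraphy using a paired" McNemar's test. It gives no time point, unit of analysis (patient or lesion), significance level or sidedness for this test.

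Bone-scan status at entry is fixed by eligibility. Inclusion criterion 4 (Section 5.A) states "Patients must not have definitive evidence of metastases as determined by CT of the abdomen/pelvis and bone scintigraphy (bone scan". Its note admits patients with lesions on sensitive PET methods as long as those lesions do not meet CT size criteria "and/or are not independently observed on bone scan". Exclusion criterion 8 (Section 5.B) adds "Patients must not have evidence of bone metastases or lymph node involvement as determined by bone scan or CT scan".

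Section 9.D describes how a NaF lesion is called: "Metastatic prostate cancer lesions in bone will first be localized and identified based on functional NaF PET uptake", helped by the CT anatomy, with segmentation adjusted under physician guidance. NaF scans are planned at baseline, week 12 and week 24 in patients selected for this part of the study, whose number is not given. Bone scan is repeated at week 24 (Section 8.K). For a similar cohort, Section 2.F reports that "only 4 of 34 did not have a lesion identified at baseline".

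**The concern.** A McNemar test compares two discordant counts: patients positive only on NaF (b) and patients positive only on bone scan (c). It is informative when either count could be the larger. At baseline, c is emptied by the entry criteria before any data are seen, so the p-value depends only on how many patients NaF calls positive.

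Sensitivity is also a proportion among patients who truly have bone metastases. Without a rule for who those patients are, the test compares how often each scan is read as positive. A method that over-calls is rewarded in exactly the same way as one that finds real disease. Exclusion criterion 8 and Section 6.B decline to treat a lesion seen only on NaF as metastatic disease, yet this test would count it as a successful detection.

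At stake is a very small p-value labelled as a difference in sensitivity, when much of it reflects who was allowed into the trial.

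**Working it through.** The plan states no sample size, power or expected result for this comparison, so there is no figure to reproduce.

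**Inputs.** Bone-scan-negative entry: inclusion criterion 4 and exclusion criterion 8. Earlier baseline NaF rate: (34 − 4)/34 = 30/34 = 88.2%, exact 95% interval 72.5% to 96.7% (Section 2.F). Trial size: 21 after stage 1 and 41 in total (Section 10.C), used only as upper bounds for the unstated number of NaF patients. Significance level: two-sided 0.05, my assumption.

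**Step 1: can sensitivity be formed?** Sensitivity = true positives / all patients with metastasis. If entry CT and bone scan are the reference, no patient has metastasis and the ratio is 0/0. If NaF is the reference, NaF scores 100% by construction. The documents offer no third standard.

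**Step 2: the baseline table, per patient.**

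| | Bone scan positive | Bone scan negative |
|---|---|---|
| NaF positive | 0 by eligibility | b |
| NaF negative | c = 0 by eligibility | n − b |

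**Step 3: what reaches significance.** With c = 0, exact two-sided p = 2 × (1/2)^b.

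- b = 5: p = 0.0625
- b = 6: p = 0.031
- b = 36: p = 2.9 × 10⁻¹¹ (41 × 30/34 ≈ 36, if all 41 patients had NaF scans)

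Continuity-corrected chi-square, (b − 1)²/b, also needs b ≥ 6. Uncorrected chi-square, which equals b, needs b ≥ 4. The exact one-sided test needs b ≥ 5.

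**Step 4: chance of declaring NaF superior.** This is P(B ≥ 6), with B binomial(n, q) and q the rate at which NaF is called positive, rightly or wrongly.

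| NaF patients n | q = 10% | 20% | 30% | 50% | 72.5% | 88.2% |
|---|---|---|---|---|---|---|
| 10 | <0.1% | 0.6% | 4.7% | 37.7% | 88.9% | 99.7% |
| 15 | 0.2% | 6.1% | 27.8% | 84.9% | 99.8% | >99.9% |
| 21 | 1.4% | 23.1% | 63.7% | 98.7% | >99.9% | >99.9% |
| 41 | 22.3% | 85.6% | 99.3% | >99.9% | >99.9% | >99.9% |

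The truth of the calls does not enter. A 50% call rate with no true metastasis gives 98.7% at n = 21, as would a 50% rate that was entirely correct.

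**Step 5: week 24, where c can exceed zero.** Take c = 5% as an assumption. If 20% of patients are positive on NaF only, the chance of a significant result for NaF is 10.9% (n = 21) or 37.6% (n = 41). If 50% are, it is 81.1% or 99.1%. Here the result depends on the data in both directions.

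**The case against.** Several points on the other side stand.

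A reader might infer that eligibility makes the test declare NaF superior whatever the truth. The documents do not support that. Eligibility fixes the direction, not the significance: at n = 21 and a 10% call rate the chance is 1.4%, and with fewer than six NaF-positive patients the exact two-sided test cannot reject.

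Nor is the test confined to baseline. In Section 10.D(4) the second imaging question says baseline; the McNemar sentence does not. The week 24 pair is not fixed by entry. The p-value for 36 of 41 is only an upper-bound illustration, since NaF is done in a selected subset at designated sites and the trial may stop at 21.

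The empty cells are a patient-level argument and may not be perfectly empty. Inclusion criterion 4 bars definitive evidence of metastases and exclusion criterion 8 bars evidence, so equivocal bone scans may exist.

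It would also go too far to say that objective 4 cannot be answered. Counting NaF-positive patients among bone-scan-negative ones addresses it directly, and a table is already planned. Nor do the documents suggest that the NaF lesions are benign. They give no false-positive rate, and calls are assisted by CT and physician guidance.

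Finally, the analysis is exploratory, and NaF results are barred from eligibility, progression and treatment decisions.

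What this does not remove is the missing reference standard, which applies at every time point. Section 2.F assumes that these patients have metastases below the detection limit, but that is an assumption about patients and verifies no bone lesion.

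**Conclusion.** The point holds in this form. The planned comparison does not measure sensitivity because no reference standard is named, and at baseline, per patient, it can only favour NaF or be inconclusive. Under an assumed two-sided 0.05 level, six NaF-positive patients are enough. If the 88.2% rate carries over, significance is 99.7% likely with 10 NaF patients and practically certain with 15 or more. At the lower confidence limit of 72.5%, the figures are 88.9% with 10 and 99.8% with 15. At low call rates the outcome is open.

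These sizes rest on a baseline, patient-level reading, no equivocal bone scans counted as positive, and a number of NaF patients that the plan does not give. No primary or secondary conclusion is affected. The correction is still worth making, because this is the only formal test planned for objective 4 and its p-value would be easy to misread.

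**What to change.** In Section 10.D(4), and in the detailed SAP that Section 10.D(1) promises:

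1. At baseline, drop the McNemar test. Report the proportion of bone-scan-negative patients who are NaF-positive with a Wilson 95% confidence interval, the method already chosen for toxicity rates. State how equivocal bone scans are classified and how many patients had NaF scans.
2. Limit any paired test to the week 24 NaF and bone scan pair, with the patient as the unit and a stated significance level. Call it a comparison of positivity, or detection rate. Note that patients who progressed earlier have left the study (Section 6.B), so this pair is still partly selected.
3. Leave the clinical meaning of baseline NaF lesions to the patient-level Cox and logistic analyses of later progression already planned in the same section.

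These changes cost wording only; no scan is added. Lesion-level confirmation on later bone scans should be optional and descriptive. A reader might assume that it is already provided for, but Section 9.D plans lesion matching only across NaF scans, so it would need a new procedure. It would also be a weak reference: patients are on active treatment and bone scan is the comparator itself, so non-confirmation would not show that a NaF lesion was false.
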